10.9. Intraocular Pressure

IOP results will be categorized as <18, 18-25, or >25 mmHg separately in the study eye and non-study eye and summarized using a shift table. Results will be listed chronologically by patient and visit.

10.10. Meibography/Meiboscopy

Meibography results will be collected in each eye and summarized using a shift table.

11. INTERIM ANALYSES

No official interim analysis will be performed.

As described in [Section 1.2](#) and [Section 2.3.2](#), a sample size re-estimation will be performed, in a masked fashion, after all patients complete Month 3. These analyses will be limited to calculation of pooled standard deviations for MGYLS and OSDI total score, and the sample size re-estimation using pseudocode presented in [Section 2.3.2](#). No data summaries or comparisons between treatment groups will be created, and no unmasking will occur.

- The subgroup analyses specified in [AZ201801 Protocol Section 9.4.7](#) are not utilized in the Expansion Cohort analyses.

- Urine pregnancy test results will not be evaluated as a safety endpoint.

14. PROGRAMMING CONSIDERATIONS

All statistical computations and construction of tables and listings will be performed using SAS[®] for Windows Version 9.4 or higher (SAS[®] Institute Inc., Cary, NC, USA).

The table and listing shells will be developed in a separate document and approved by the sponsor and other stakeholders. Any subsequent changes determined to be necessary will be documented and approved by the sponsor and statistical team. SDTM datasets will be created from the clinical database and external data, following the Study Data Tabulation Model Implementation Guide version 3.2 or higher. Analysis will be based on ADaM datasets created from the SDTM datasets and will follow the Analysis Dataset Model Implementation Guide version 1.3 or higher.

Patient participation will be ongoing at the time of the analyses based on Month 3 data, and some patients could have already completed the Month 4.5 and/or Month 6 visits at that time. At the time of the Month 3 sample size re-estimation, data necessary for the re-estimation (e.g., Screening and Baseline visit information and all MGYLS and OSDI assessments through Month 3) will be fully cleaned for all patients. At the time of the Month 3 database freeze, data will be fully cleaned through the Month 3 visit for all patients. All patient information in the database will be transferred to the statistical team for analyses. The statistical team will programmatically limit the data used in analysis datasets, tables, and listings to the information collected through Month 3, including any unscheduled visits collected during that time and any early termination visits in subjects who did not have a Month 3 visit. Tables and listings presenting information such as disposition, adverse events, medications, and other information not summarized in a by-visit fashion will be presented through Month 3.

Any adverse events that are ongoing at the Month 3 visit and resolve after the Month 3 visit, even if resolution information has been entered in the database at the time of database freeze, will programmatically have the stop date removed, be categorized as Ongoing, and have

outcome assigned to Not Yet Resolved. Any patients who do not have a Month 3 visit but are not discontinued (i.e., did not attend Month 3 visit but remained on trial) will utilize the expected date of the Month 3 visit in this algorithm.

Similarly, non-study medications (e.g., prior and concomitant) that are ongoing at the Month 3 visit and have end date information entered in the database from a later study visit (e.g., Month 4.5 or 6) at the time of database freeze, will be programmatically have stop date removed, and be categorized as Ongoing.

After all patients have completed the Month 6 visit (e.g., completed the safety follow-up period), all patient data after the Month 3 visit will be fully cleaned, and the database locked.

14.1. General Considerations

- One SAS program can create multiple tables (or listings). One program is expected to create both the 3-month and 6-month output (e.g., one program is used to create both Table 17 and Table 17.1, or to create Listing 1 and Listing 1.1).
- Output files will be delivered in Word format. Tables and listings (TLs) will be bundled separately with a table of contents for each.

14.2. Table and Listing Formatting

14.2.1. General

- All TLs will be produced in landscape format, using the Courier New font, size 8 with approximately 1-inch margin on all 4 sides.
- Each table or listing will have a solid line at the top, one underneath the column headers, and one underneath the body of the text.

14.2.2. Headers

- All output should have the following header at the top left of each page:

Protocol AZ201801 Expansion Cohort
Azura Ophthalmics

- All output should have **Page n of N** at the top right corner of each page. TLs should be internally paginated in relation to the total length (i.e., the page number should appear sequentially as page n of N, where N is the total number of pages in the table).

14.2.3. Display Titles

- The titles should be formatted as follows, with the title text wrapping to a second line where necessary. The title and table designation will be single spaced. Listings will include all available data and will not have an analysis set displayed.

Table x
Title Text
(Analysis Set)

14.2.4. Body of the Data Display

14.2.4.1. General Conventions

Data in the body of a table or listing are formatted as follows:

- Alphanumeric values that do not wrap are centered; those that do wrap are left-justified
- Whole numbers (e.g., counts) are centered
- Numbers containing fractional portions are decimal aligned or centered, as appropriate.

14.2.4.2. Table Conventions

- Analysis population sizes will be presented for each treatment group in the column heading as (N=xx) (or in the row headings if applicable). This is distinct from the ‘n’ used for the descriptive statistics representing the number of patients in the analysis population.
- If the categories of a parameter are ordered, then all categories between the maximum and minimum category are presented in the table, even if n=0 for all treatment groups in a given category that is between the minimum and maximum level for that parameter.
- Where percentages are presented in these tables, zero percentages will not be presented; that is, it will be presented as 0 and not as 0 (0%).
- An Unknown or Missing category are added to each parameter for which information is not available for 1 or more patients.
- Percentage values are printed to one decimal place, in parentheses with no spaces, one space after the count (e.g., 7 (12.8), 13 (5.4)). Values that round to 0.0 will be displayed as 0.0. Percentages equating or rounding to 100% are presented as 100, without decimal places. Percent sign may be indicated in column header or row label and not displayed in the body of the results, or included in the results (e.g., 7 (12.8%)) as indicated in the shells.
- Missing descriptive statistics or p-values which cannot be estimated are reported as “N/E”.

- The percentage of patients is normally calculated as a proportion of the number of patients assessed in the relevant treatment group (or overall) in the column header. If the percentage is calculated based on a different number, it will be indicated with a footnote (such as in a disposition table) or with the inclusion of a “n” line reflecting the denominator (such as a by-visit analysis).

14.2.4.3. Listing Conventions

- Assessments collected at the early termination visit (recorded as occurring at Month 6, where the assessment date is equal to the End of Study visit date [in the Subject Visits dataset] or the date of early termination [recorded as the date of completion or early termination on the End of Study eCRF page, where study completion status is no]) will be relabeled to “Early Term” in the listings. Any assessments recorded as a scheduled visit other than Month 6 will not be relabeled in this manner.
- Missing data will be left blank, unless otherwise specified.
- Dates are printed in SAS DATE9.format (“ddMMMyyyy”: 01JUL2000). Missing portions of dates may be represented on patient listings as dashes (--JUL2000). Dates that are missing because they are not applicable for the patient will be left blank, unless otherwise specified.
- All observed time values are to be presented using a 24-hour clock HH:MM or HH:MM:SS format (e.g., 11:26, or 11:26:45). Time will only be reported if it was measured as part of the study.
- Where data is presented by study eye vs. non-study eye, patients without study eye assigned (i.e., unrandomized patients) will have the right eye displayed in the study eye column(s) and left eye displayed in the non-study eye column(s), as indicated in footnotes.

14.2.5. Footnotes

- All footnotes will be left justified with single-line spacing immediately below the solid line underneath the data display.
- Footnotes should always begin with “Note:” if an informational footnote, or [a], [b], etc. if a reference footnote. Each new footnote should start on a new line, where possible.
- The last line of the footnote section will be a standard source line that indicates the name of the program used to produce the data display, date the program was run, whether it is draft or final, and the listing source (i.e., ‘Program : myprogram.sas DRAFT Listing source: xxx).

15. APPENDICES

Appendix 1 Visual Analogue Scale (VAS)

Burning/Stinging	0%	50%	100%

Itching	0%	50%	100%

Foreign body sensation	0%	50%	100%

Eye Discomfort	0%	50%	100%

Eye Dryness	0%	50%	100%

Photophobia	0%	50%	100%

Pain	0%	50%	100%

Appendix 2 Ocular Surface Disease Index (OSDI)

OCULAR SURFACE DISEASE INDEX ©
 (US English version of the OSDI)

Please answer the following questions by checking the box that best represents your answer.

Have you experienced any of the following during the last week:

		All of the time	Most of the time	Half of the time	Some of the time	None of the time
1	Eyes that are sensitive to light?					
2	Eyes that feel gritty?					
3	Painful or sore eyes?					
4	Blurred vision?					
5	Poor vision?					

Have problems with your eyes limited you in performing any of the following during the last week:

		All of the time	Most of the time	Half of the time	Some of the time	None of the time	Not applicable
6	Reading?						
7	Driving at night?						
8	Working with a computer or bank machine (ATM)?						
9	Watching TV?						

Have your eyes felt uncomfortable in any of the following situations during the last week:

		All of the time	Most of the time	Half of the time	Some of the time	None of the time	Not applicable
10	Windy conditions?						
11	Places or areas with low humidity (very dry)?						
12	Areas that are air conditioned?						

Copyright © 1995 Allergan, Inc.

Appendix 3 Standard Patient Evaluation of Eye Dryness (SPEED) Questionnaire

SPEED™ QUESTIONNAIRE

Name: _____ Date: ___/___/___ Sex: M F (Circle) DOB: ___/___/___

For the Standardized Patient Evaluation of Eye Dryness (SPEED) Questionnaire, please answer the following questions by checking the box that best represents your answer. Select only one answer per question.

1. Report the type of SYMPTOMS you experience and when they occur:

Symptoms	At this visit		Within past 72 hours		Within past 3 months	
	Yes	No	Yes	No	Yes	No
Dryness, Grittiness or Scratchiness						
Soreness or Irritation						
Burning or Watering						
Eye Fatigue						

2. Report the FREQUENCY of your symptoms using the rating list below:

Symptoms	0	1	2	3
Dryness, Grittiness or Scratchiness				
Soreness or Irritation				
Burning or Watering				
Eye Fatigue				

0 = Never 1 = Sometimes 2 = Often 3 = Constant

3. Report the SEVERITY of your symptoms using the rating list below:

Symptoms	0	1	2	3	4
Dryness, Grittiness or Scratchiness					
Soreness or Irritation					
Burning or Watering					
Eye Fatigue					

0 = No Problems
 1 = Tolerable - not perfect, but not uncomfortable
 2 = Uncomfortable - irritating, but does not interfere with my day
 3 = Bothersome - irritating and interferes with my day
 4 = Intolerable - unable to perform my daily tasks

4. Do you use eye drops for lubrication? YES NO If yes, how often? _____

Cornea. 2013 Sep;32(9):1204-10
 © 2011 TearScience, Inc. All rights reserved.
 13-ADV-123 A

For office use only
 Total SPEED score (Frequency + Severity) = ___/28

Appendix 4 List of Tables and Listings Produced at the 3 Month Analysis

The following tables and listings will be produced at Month 3. Shells are provided for each unique table and listing in a separate document.

Comprehensive efficacy and safety analyses will be produced after the completion of the Month 3 visits. Additional safety information will be collected through the Month 6 visit and presented in supplemental safety tables and listings.

Table 1 Summary of Patient Disposition Through Month 3 – Expansion Cohort (All Patients)

Table 2A Summary of Demographic and Baseline Characteristics – Expansion Cohort (Safety Set)

Table 2B Summary of Demographics and Baseline Characteristics – Expansion Cohort (ITT Analysis Set)

Table 2C Summary of Demographics and Baseline Characteristics – Expansion Cohort (mITT Analysis Set)

Table 2D Summary of Demographics and Baseline Characteristics – Expansion Cohort (Per-Protocol Set)

Table 3A Summary of Ophthalmic Medical History – Expansion Cohort (Safety Set)

Table 3B Summary of Ophthalmic Medical History – Expansion Cohort (ITT Set)

Table 3C Summary of Ophthalmic Medical History – Expansion Cohort (mITT Set)

Table 3D Summary of Ophthalmic Medical History – Expansion Cohort (Per-Protocol Set)

Table 4A Summary of Non-Ophthalmic Medical History – Expansion Cohort (Safety Set)

Table 4B Summary of Non-Ophthalmic Medical History – Expansion Cohort (ITT Set)

Table 4C Summary of Non-Ophthalmic Medical History – Expansion Cohort (mITT Set)

Table 4D Summary of Non-Ophthalmic Medical History – Expansion Cohort (Per-Protocol Set)

Table 5A Summary of Protocol Deviations by Grade Through Month 3 – Expansion Cohort (Safety Set)

Table 5B Summary of Protocol Deviations by Grade Through Month 3 – Expansion Cohort (ITT Analysis Set)

Table 5C Summary of Protocol Deviations by Grade Through Month 3 – Expansion Cohort (mITT Analysis Set)

Table 5D Summary of Protocol Deviations by Grade Through Month 3 – Expansion Cohort (Per-Protocol Set)

Table 6A Analysis of Meibomian Glands Yielding Liquid Secretion (MGYLS) Through Month 3 – Expansion Cohort (ITT Analysis Set)

Table 6B Analysis of Meibomian Glands Yielding Liquid Secretion (MGYLS) Through Month 3 – Expansion Cohort (mITT Analysis Set)

Table 6C Analysis of Meibomian Glands Yielding Liquid Secretion (MGYLS) Through Month 3 – Expansion Cohort (PP Analysis Set)

Table 6D Sensitivity Analysis of Meibomian Glands Yielding Liquid Secretion (MGYLS), based on LOCF Imputation Through Month 3 – Expansion Cohort (ITT Analysis Set)

Table 7A Analysis of Ocular Surface Disease Index (OSDI) Total and Subscale Results Through Month 3 – Expansion Cohort (ITT Analysis Set)

Table 7B Analysis of Ocular Surface Disease Index (OSDI) Total and Subscale Results Through Month 3 – Expansion Cohort (mITT Analysis Set)

Table 7C Analysis of Ocular Surface Disease Index (OSDI) Total and Subscale Results Through Month 3 – Expansion Cohort (PP Analysis Set)

Table 7D Sensitivity Analysis of Ocular Surface Disease Index (OSDI) Total and Subscale Results, based on LOCF Imputation Through Month 3 – Expansion Cohort (ITT Analysis Set)

Table 8 Analysis of Standard Patient Evaluation of Eye Dryness (SPEED) Through Month 3 – Expansion Cohort (ITT Analysis Set)

Table 9 Analysis of Visual Analogue Scale (VAS) Results Through Month 3 – Expansion Cohort (ITT Analysis Set)

Table 10 Analysis of Meibomian Gland Score Through Month 3 – Expansion Cohort (ITT Analysis Set)

Table 11 Analysis of Tear Break-up Time (TBUT) Through Month 3 – Expansion Cohort (ITT Analysis Set)

Table 12 Analysis of Meibomian Glands Yielding Optimal Liquid Secretion (MGYOLS) Through Month 3 – Expansion Cohort (ITT Analysis Set)

Table 13 Analysis of Schirmer's Test without Anesthesia Through Month 3 – Expansion Cohort (ITT Analysis Set)

Table 14 Analysis of Responder Status Through Month 3 – Expansion Cohort (ITT Analysis Set)

Table 15A Shift Table and Analysis of Slit Lamp Results, Including Erythema, Telangiectasias, and Conjunctival Hyperemia Through Month 3 (ITT Analysis Set)

Table 15B Shift Table of Slit Lamp Results for Anterior Chamber Cells Through Month 3 (ITT Analysis Set)

Table 15C Shift Table of Slit Lamp Results for Anterior Chamber Flare Through Month 3 (ITT Analysis Set)

Table 15D Shift Table of Slit Lamp Results for Anterior Chamber Iris and Pupil Through Month 3 (ITT Analysis Set)

Table 16 Shift Table of Sodium Fluorescein and Lissamine Green Staining Results Through Month 3 – Expansion Cohort (Safety Set)

Table 17 Randomized Study Treatment Exposure and Compliance Through Month 3 – Expansion Cohort (Safety Set)

Table 18 Overall Summary of Treatment-Emergent Adverse Events Through Month 3 – Expansion Cohort (Safety Set)

Table 19 Summary of Treatment-Emergent Adverse Events, by System Organ Class and Preferred Term Through Month 3 – Expansion Cohort (Safety Set)

Table 20 Summary of Treatment-Emergent Adverse Events Attributed to Vaseline Application at Baseline, by System Organ Class and Preferred Term – Expansion Cohort (Pre-Randomization Vaseline Application Set)

Table 21 Summary of Ophthalmic Treatment-Emergent Adverse Events, by System Organ Class and Preferred Term Through Month 3 – Expansion Cohort (Safety Set)

Table 22 Summary of Ophthalmic Treatment-Emergent Adverse Events, in Study Eye by System Organ Class and Preferred Term Through Month 3 – Expansion Cohort (Safety Set)

Table 26 Summary of Ophthalmic Treatment-Emergent Adverse Events, in Non-Study Eye by System Organ Class and Preferred Term Through Month 3 – Expansion Cohort (Safety Set)

Table 24 Summary of Non-Ophthalmic Treatment-Emergent Adverse Events, by System Organ Class and Preferred Term Through Month 3 – Expansion Cohort (Safety Set)

Table 25 Summary of Serious Treatment-Emergent Adverse Events, by System Organ Class and Preferred Term Through Month 3 – Expansion Cohort (Safety Set)

Table 26 Summary of Treatment-Emergent Adverse Events Leading to Study Drug Withdrawal, by System Organ Class and Preferred Term Through Month 3 – Expansion Cohort (Safety Set)

Table 27 Summary of Treatment-Emergent Adverse Events Possibly, Probably, or Certainly Related to Study Intervention, by System Organ Class and Preferred Term Through Month 3 – Expansion Cohort (Safety Set)

Table 28 Summary of Treatment-Emergent Adverse Events by Preferred Term Through Month 3 – Expansion Cohort (Safety Set)

Table 29 Summary of Treatment-Emergent Adverse Events, by System Organ Class, Preferred Term and Severity Through Month 3 – Expansion Cohort (Safety Set)

Table 30 Summary of Treatment-Emergent Adverse Events, by System Organ Class, Preferred Term and Relationship Through Month 3 – Expansion Cohort (Safety Set)

Table 31 Summary of Treatment-Emergent Adverse Events, by System Organ Class, Preferred Term and Site Through Month 3 – Expansion Cohort (Safety Set)

Table 32 Summary of Concomitant Medication Through Month 3 – Expansion Cohort (Safety Set)

Table 33 Summary of Best Corrected Visual Acuity (BCVA) Results Through Month 3 – Expansion Cohort (Safety Set)

Table 34 Summary of Vital Signs Through Month 3 – Expansion Cohort (Safety Set)

Table 35A Shift Table of Ophthalmoscopy Lens Status Through Month 3 – Expansion Cohort (Safety Set)

Table 35B Shift Table of Ophthalmoscopy Details Through Month 3 – Expansion Cohort (Safety Set)

Table 36 Shift Table of Intraocular Pressure Through Month 3 – Expansion Cohort (Safety Set)

Table 37 Shift Table of Meibography/Meiboscopy Results Through Month 3 – Expansion Cohort (Safety Set)

Listing 1 Patient Disposition and Analysis Set Inclusion Through Month 3 – Expansion Cohort

Listing 2 Inclusion and Exclusion Criteria Not Met and Screen Failure Information – Expansion Cohort

Listing 3 Patient Demographics and Baseline Characteristics – Expansion Cohort

Listing 4 Ophthalmic Medical History – Expansion Cohort

Listing 5 Non-Ophthalmic Medical History – Expansion Cohort

Listing 6 Grade 2 or Higher Protocol Deviations Through Month 3 – Expansion Cohort

Listing 7 Patient Visits Through Month 3 – Expansion Cohort

Listing 8 Meibomian Gland Evaluation (MGS, MGYLS, MGYOLS) Through Month 3 – Expansion Cohort

Listing 9 Ocular Surface Disease Index (OSDI) Through Month 3 – Expansion Cohort

Listing 10 Standard Patient Evaluation of Eye Dryness (SPEED) Through Month 3 – Expansion Cohort

Listing 11 Visual Analogue Scale (VAS) Responses Through Month 3 – Expansion Cohort

Listing 12 Tear Break-up Time (TBUT) Through Month 3 – Expansion Cohort

Listing 13 Schirmer's Assessment Results, without Anesthesia, Through Month 3 – Expansion Cohort

Listing 14 Slit Lamp Examination, Including Erythema, Telangiectasias, and Conjunctival Hyperemia Through Month 3 – Expansion Cohort

Listing 15 Lissamine Green and Sodium Fluorescein Staining, Oxford Scale Through Month 3 – Expansion Cohort

Listing 16 Study Drug Dispensation, Return and Compliance Through Month 3 – Expansion Cohort

Listing 17 Physician Observation of Vaseline Application at Baseline Visit

Listing 18A Adverse Events Through Month 3 – Expansion Cohort

Listing 18B Serious Adverse Events Through Month 3 – Expansion Cohort

Listing 18C Adverse Events Leading to Drug Withdrawal Through Month 3 – Expansion Cohort

Listing 18D Adverse Events Due to Vaseline Application at Baseline Visit– Expansion Cohort

Listing 19 Prior and Concomitant Ophthalmic Medications Through Month 3 – Expansion Cohort

Listing 20 Prior and Concomitant Non-Ophthalmic Medications Through Month 3 – Expansion Cohort

Listing 21 Urine Pregnancy Test Results Through Month 3 – Expansion Cohort

Listing 22 Best Corrected Visual Acuity (BCVA) Through Month 3 – Expansion Cohort

Listing 23 Vital Signs Through Month 3 – Expansion Cohort

Listing 24 Ophthalmoscopy Results Through Month 3 – Expansion Cohort

Listing 25 Intraocular Pressure Through Month 3 – Expansion Cohort

Listing 26 Meibography/Meiboscopy Results Through Month 3 – Expansion Cohort

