4. ANALYSIS SETS

4.1. Intent-to-Treat Analysis Set

The Intent-to-Treat (ITT) Set will include all patients who were randomized. Patients will be analyzed according to treatment as randomized. The ITT Set will be used for analyses of efficacy data.

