4.6. Safety Set

The Safety Set will include all patients who were administered at least one dose of randomized study medication. Patients will be analyzed according to treatment received. The Safety Set will be used for all analyses of safety data.

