8.3. Exploratory Efficacy Analyses

The following endpoints will be presented using the ITT Set, unless otherwise specified. Where applicable, actual values and changes from baseline will be summarized descriptively for all time points at which the endpoint is collected.

8.3.1. Exploratory Efficacy Analyses Performed at Month 3

Proportion of MGYLS responders based on MGYLS > 2 will be analyzed through Month 3 as described for the proportion of MGYLS responders, using a CMH test (or chi-square/Fisher's Exact if CMH is not estimable) to evaluate the difference between treatments, controlling for duration of disease category and baseline MGS score category.

Change from baseline in MGYOLS at Day 14, Month 1.5 and Month 3 will be analyzed as described for MGYLS in [Section 8.1.1](#).

Proportion of MGYOLS responders based on MGYOLS >2 will be analyzed through Month 3 as described for the proportion of MGYLS responders, using a CMH test (or chi-square/Fisher's Exact if CMH is not estimable) to evaluate the difference between treatments, controlling for duration of disease category and baseline MGS score category.

Proportion of OSDI responders based on a reduction of >4.5 will be analyzed through Month 3 as described for the proportion of MGYLS responders, using a CMH test (or chi square/Fisher's Exact if CMH is not estimable) to evaluate the difference between treatments, controlling for duration of disease category and baseline MGS score category.

Change from baseline in OSDI subscales at Day 14, Month 1.5 and Month 3 will be analyzed as described for MGYLS in [Section 8.1.1](#).

Proportion of SPEED responders based on SPEED <6 will be analyzed through Month 3 as described for the proportion of MGYLS responders, using a CMH test (or chi-square/Fisher's Exact if CMH is not estimable) to evaluate the difference between treatments, controlling for duration of disease category and baseline MGS score category.

Change from baseline in TBUT at Day 14, Month 1.5 and Month 3 will be analyzed as described for MGYLS in [Section 8.1.1](#).

Proportions of TBUT >5 and >10 responders will be analyzed through Month 3 as described for the proportion of MGYLS responders, using a CMH test (or chi-square/Fisher's Exact if

CMH is not estimable) to evaluate the difference between treatments, controlling for duration of disease category and baseline MGS score category.

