10. SAFETY

The Safety Set will be used for safety analyses reports. Safety will be assessed based on adverse events, vital signs, BCVA (Logarithmic visual acuity chart), biomicroscopy, ophthalmoscopy, IOP, and conjunctival hyperemia (redness).

The primary safety analysis will be performed after all patients have completed the Month 3 visit or discontinued from the study. An additional 3-month safety follow-up (including Month 4.5 and Month 6 visits) will be conducted, and supplemental safety results will be produced after the completion of the Month 6 visits.

A combined analysis of Cohort 1 and Expansion Cohort data will not be produced, as Cohort 1 includes different dosing regimens (once daily vs. twice weekly) as well as including different treatments (AZR-MD-001 0.1%, vehicle).

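### The table lists in SAP Appendices 4 and 5 put slit-lamp safety content only on the ITT Set and the staining efficacy tables only on the Safety Set, against the SAP's own analysis-set rules

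*SAP*

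**What the plan says.** SAP Section 4.1 on the ITT Set: "Patients will be analyzed according to treatment as randomized. The ITT Set will be used for analyses of efficacy data".

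SAP Section 4.6 on the Safety Set, which holds patients dosed at least once: "Patients will be analyzed according to treatment received. The Safety Set will be used for all analyses of safety data".

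SAP Section 10 repeats the rule for the safety outputs and lists what counts as safety: "Safety will be assessed based on adverse events, vital signs, BCVA (Logarithmic visual acuity chart), biomicroscopy, ophthalmoscopy, IOP, and conjunctival hyperemia (redness". Section 3.2 gives the same list of endpoints. Section 10.7 again labels hyperemia a safety endpoint and, within the slit-lamp results, treats only study-eye erythema and telangiectasias as exploratory efficacy.

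Corneal and conjunctival staining appears among the exploratory efficacy endpoints (Sections 3.1.3.1 and 3.1.3.2) and not among the safety endpoints. Section 8.3 sets the default for such endpoints: "The following endpoints will be presented using the ITT Set, unless otherwise specified". Section 8.3.1 plans a CMH comparison for staining and names no other set.

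The table lists read differently. In Appendix 4 the staining title (number 16), "Shift Table of Sodium Fluorescein and Lissamine Green Staining Results Through Month 3", carries the Safety Set. The slit-lamp tables 15A to 15D are all on ITT, for example "Shift Table of Slit Lamp Results for Anterior Chamber Cells Through Month 3 (ITT Analysis Set". Appendix 5 makes the same assignments for Tables 15A.1 to 15D.1 and 16.1. Neither appendix lists a slit-lamp table on the Safety Set or a staining table on ITT.

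**The concern.** A programmer working from the appendices would run the slit-lamp safety tables on a population, and with an arm assignment, that Sections 4.6 and 10 do not allow for safety data. The reverse would happen for staining.

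The two sets differ in membership and in arm. If a patient were given a treatment other than the one assigned, that patient's hyperemia or anterior-chamber finding would be counted in the assigned arm, while an ophthalmic adverse event in the same eye would be counted in the arm actually received, because the adverse-event tables are on the Safety Set. For staining, the only listed output would group patients by treatment received, so the as-randomized comparison that the efficacy rules call for would have no listed table.

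**Working it through.** No figure is at stake, so the check compares rules, endpoint classes and table titles.

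**Step 1. Rules.** Efficacy: ITT, all randomized, by assigned arm (SAP 4.1, 8, 8.3). Safety: Safety Set, dosed patients, by arm received (SAP 4.6, 10). Protocol Section 9.2 agrees that safety variables follow the treatment actually received.

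**Step 2. Endpoint class against the listed set.**

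| Tables | Content | Class in the SAP | Set required | Set listed | Agree? |
|---|---|---|---|---|---|
| 15A, 15A.1 | Eyelid margin erythema, telangiectasias | Exploratory efficacy (3.1.3, 10.7) | ITT | ITT | Yes |
| 15A, 15A.1 | Conjunctival hyperemia | Safety (3.2, 10, 10.7) | Safety | ITT | No |
| 15B, 15B.1 | Anterior chamber cells | Safety, as biomicroscopy (3.2, 10) | Safety | ITT | No |
| 15C, 15C.1 | Anterior chamber flare | Safety, as biomicroscopy (3.2, 10) | Safety | ITT | No |
| 15D, 15D.1 | Iris and pupil | Safety, as biomicroscopy (3.2, 10) | Safety | ITT | No |
| 16, 16.1 | Corneal and conjunctival staining | Exploratory efficacy (3.1.3, 8.3) | ITT | Safety | No |

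The protocol classes these items the same way: biomicroscopy is a safety measure (Section 8.2.1) and staining an efficacy measure (Section 8.1.5).

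**Step 3. Comparison with neighbouring tables.** In Appendix 4 the other ocular safety tables, for BCVA (33), ophthalmoscopy (35A, 35B) and IOP (36), are on the Safety Set. The efficacy tables 6 to 14 are on ITT, mITT or PP. The slit-lamp and staining tables are therefore the exceptions.

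**Step 4. Is an exception declared?** No body section moves slit-lamp safety findings to ITT or staining to the Safety Set. SAP Section 12, which records departures from the protocol, mentions neither.

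**Step 5. Who is affected?** From the two set definitions, results differ only for:

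- patients randomized but never dosed, who are in ITT but not in the Safety Set;
- patients who received a treatment other than the one assigned, who are in both sets but in different arms.

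The SAP allows for both. Section 5.2.1 covers patients without confirmed dosing, and Section 5.1 provides a listing footnote where actual and randomized treatment differ. Neither document gives a count. If every randomized patient was dosed as assigned, the two sets coincide and every table is unchanged.

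**The case against.** The best defence is that the ITT label on the Table 15 family has some footing in the body text. Section 8.3.1, under the ITT default, reports erythema and telangiectasias together with the remaining slit-lamp findings, and Section 10.7 refers back to Section 8.3 for the shift tables. On that reading the SAP gives two answers and the appendices chose one. Part of this stands: ITT is correct for the erythema and telangiectasia content of 15A and 15A.1. The rest does not settle the matter. The cross-reference in Section 10.7 concerns how the shift table is built, and that section sits under Section 10, which opens by setting the Safety Set. Two answers would in any case need reconciling.

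For staining, one could say that the Table 16 title is itself the exception that Section 8.3 permits. This is weak, because no text states or explains such an exception.

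It is also fair to say that the practical risk is limited. Kits are assigned through the IWRS, and Listings 14 and 15 show the individual slit-lamp and staining records, with a footnote where actual treatment differs. This reduces the consequence but does not remove the contradiction.

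**Conclusion.** The appendices conflict with the SAP's analysis-set rules for hyperemia and the anterior-chamber tables in one direction and for staining in the other. This is a minor consistency error in safety and exploratory output. It leaves the primary and key secondary analyses untouched, and it changes a number only if some patients were undosed or received a treatment other than the one assigned.

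Three stronger readings are tempting but not supported:

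- **That the appendices simply swap the two sets.** They do not, because ITT is right for part of 15A and 15A.1.
- **That never-dosed patients dilute the slit-lamp rates.** SAP Section 14.2.4.2 bases percentages on patients assessed and allows a separate n line for by-visit analyses. A never-dosed patient with no post-baseline examination need not enter the denominator, and one who does attend need not have zero findings. No dilution can be computed.
- **That the staining CMH test will be run as treated.** The Table 16 title says only that it is a shift table, whereas the Table 15A title adds an analysis. The shells are in a separate document. What can be said is that the CMH comparison planned in Section 8.3.1 has no listed ITT staining table.

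**What to change.** Amend Appendices 4 and 5 and the matching shells, preferably before the Month 3 database freeze and unmasking:

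- Produce conjunctival hyperemia and Tables 15B to 15D and 15B.1 to 15D.1 on the Safety Set, by treatment received.
- Split Tables 15A and 15A.1 so that all erythema and telangiectasia output (actual values, shifts and the CMH test) stays on ITT as randomized. Moving only the CMH panel would take the shift summaries of an efficacy endpoint off ITT and create a new mismatch.
- Produce Tables 16 and 16.1 on ITT and state in the title or shell that they carry the CMH comparison from Section 8.3. A Safety Set copy may be kept as a supplement.
- Add a sentence to Section 10.7 saying that its reference to Section 8.3 covers table format only, and that the Safety Set applies to slit-lamp safety findings.

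The cost is a change to titles and shells, one table split at each of the two analysis times, and a rerun of existing programs with a different population flag and treatment variable. No new data or methods are needed.
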